11.4.4 Safety Analysis

The safety analysis will be conducted on all subjects who had at least one administration of the study drug.

Adverse events will be summarized using MedDRA terms. The incidence and severity of adverse events will be listed and grouped by body system.

All laboratory data will be listed and values falling outside normal ranges will be identified. Summary statistics (i.e., mean, median, standard deviation, minimum, and maximum) will be presented for all continuous variables.

Summary statistics will be given on the number of subjects for whom the trial medication had to be permanently stopped.

12 ADVERSE EVENTS

12.1 Definition of Adverse Events

An Adverse Event (AE) is defined as follows: Any untoward medical occurrence in a patient or subject including unfavorable and unintended signs, symptoms or disease temporally associated with the use of a medicinal product and which does not necessarily have to have a causal relationship to this treatment.

Adverse events include illnesses with onset during the trial, or exacerbations of pre-existing illnesses. Exacerbation of pre-existing illness is defined as a significant increase in the severity of the illness as compared to the start of the trial, and should be considered when a subject requires new or additional treatment for that illness. Lack of or insufficient clinical response or efficacy should not be recorded as an adverse event.

In addition, clinically significant changes in objective findings (e.g., laboratory, ECG, X-ray, physical examination) should also be considered as to whether they are adverse events. The criteria for determining whether an objective finding should be reported as an adverse event are as follows:

1. Associated with accompanying symptoms; and/or
2. Requires medical/surgical intervention; and/or
3. Leads to a change in trial dosing or discontinuation from the trial, significant additional concomitant drug treatment or other therapy; and/or
4. Leads to any of the outcomes included in the definition of a serious adverse event; and/or
5. Is considered to be an adverse event by the investigator or Sponsor.

Any abnormal test result that is determined to be an error does not require reporting as an adverse event.

12.2 Assessment and Reporting of Adverse Events

Adverse events will be recorded starting after the first dose of trial drug and continuing until 30 days after the last dose or until the last follow-up visit required by the protocol, whichever comes later. An adverse event that is ongoing at the last follow up study visit is required to be followed up until the event resolves or stabilizes at a level acceptable to the investigator and/or Sponsor.

All adverse events spontaneously reported, elicited or observed by the investigators will be recorded. The events will be recorded in the source documents and onto the adverse event pages of the case report form, including date of onset and resolution, severity, relationship to trial treatment and determination of “serious”.

Diagnostic and therapeutic non-invasive and invasive procedures, such as surgery, should not be reported as adverse events. However, the medical condition for which the procedure was performed should be reported if it meets the definition of an adverse event. For example, an acute appendicitis that begins during the adverse event reporting period should be reported as the adverse event, and the resulting appendectomy should be recorded as treatment of the adverse event.

The investigator will take all therapeutic measures necessary for resolution of the adverse event. Any medication necessary for treatment of the adverse event must be recorded in the subject’s source documents and on the appropriate pages of the subject’s case report form.

To assist with grading of adverse event severity, the following definitions are provided:

- Mild** = Aware of sign or symptom, but easily tolerated;
- Moderate** = Discomfort enough to cause interference with usual activity;
- Severe** = Incapacitating with inability to work or do usual activity;

Adverse events are assessed as either related to the intravitreal injection procedure (eyelid speculum, anesthetic drops, mydriatic drops, antibiotic drops, povidone-iodine drops or flush, subconjunctival injection of anesthetic, intravitreal injection), termed “injection procedure-related”, or to study drug (Zimura™ or Lucentis® 0.5 mg).

The relationship to the intravitreal injection procedure or to study drug will be assessed using the following definitions:

- Not Related** = There is not a reasonable possibility that the adverse event is related to the injection procedure or to the study drug.
- Related** = There is a reasonable possibility that the adverse event is related to the injection procedure or to the study drug.

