6 TRIAL DESIGN

There will be 4 dosing cohorts on this trial. Approximately 60 subjects will be enrolled; 10 subjects in cohorts 1 and 2 and 20 subjects in cohorts 3 and 4.

Cohort 1

Administered Day 1 – Month 5, in the following sequence, 2 days apart:

- D0: Lucentis[®] 0.5 mg/eye
- D2: Zimura[™] 4 mg/eye (administered as two injections of Zimura 2 mg/eye)

Cohort 2

Administered Day 1 – Month 5, in the following sequence:

- Lucentis[®] 0.5 mg/eye followed by Zimura[™] 2 mg/eye on the same day

Cohort 3

Induction Phase: Administered Day 1 – Month 2, in the following sequence, 14 days apart:

- D0: Lucentis[®] 0.5 mg/eye followed by Zimura[™] 2 mg/eye on the same day
- D14: Zimura[™] 2 mg/eye

Maintenance Phase: Administered Month 3 – Month 5, in the following sequence:

- Lucentis[®] 0.5 mg/eye followed by Zimura[™] 2 mg/eye on the same day

Cohort 4

Induction Phase: Administered Day 1 – Month 2, in the following sequence, 14 days apart:

- D0: Lucentis[®] 0.5 mg/eye followed by Zimura[™] 2 mg/eye on the same day
- D14: Zimura[™] 2 mg/eye

Maintenance Phase: Administered Month 3 – Month 5, in the following sequence, 2 days apart:

- D0: Zimura[™] 2 mg/eye

- D2: Lucentis® 0.5 mg/eye followed by Zimura™ 2 mg/eye on the same day

All subjects will have a final follow-up visit at Month 6.

The first 10 subjects will be enrolled into Cohort 1 according to the procedures noted below.

The first three subjects will be assigned to Cohort 1 (Lucentis® 0.5 mg and Zimura™ 4 mg). Once the 3rd subject completes a safety period of one week after the first dose of Zimura™ 4 mg without the occurrence of a dose limiting toxicity as defined in Section 9.2.3 Dose Limiting Toxicity, full enrollment of Cohort 1 may commence.

If a DLT occurs in one or more of the first 3 subjects assigned to Cohort 1, then the Ophthotech medical team will evaluate all available data and either discontinue Cohort 1 or enroll an additional three subjects (for a total of 6 subjects) in Cohort 1. If the three additional subjects are enrolled, and no additional DLT occurs once the second set of 3 subjects in Cohort 1 has reached one week after the first dose of Zimura™ 4 mg/eye, full enrollment of Cohort 1 may commence. If one or more DLTs occur in the second set of 3 subjects, a discussion of safety data will be held among the Ophthotech medical team to review the observed toxicities and determine whether Cohort 1 may proceed.

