10 TRIAL CONDUCT

10.1 Subject Enrollment

Before recruitment of subjects into the trial, written Institutional Review Board (IRB) or Ethics Committee (EC) approval of the protocol and informed consent must be obtained.

Subjects who meet the eligibility criteria and have provided written informed consent will be enrolled in the trial. If any inclusion or exclusion criteria are not met, treatment with trial drug should not commence without prior written approval from Ophthotech Corp. or its designee.

Written informed consent must be obtained before any of the Screening procedures listed below are performed. However, if a routine office procedure (e.g. FA, OCT) is performed to diagnose NVAMD independent of this clinical trial, and subsequently the subject provides informed consent for this study, these procedures performed prior to informed consent may be used as screening assessments for this study, provided the 14-day period of screening evaluations is respected and provided the assessments are acceptable to the standards of the study. An explanation of the trial and discussion of the possible risks and discomforts will be given by the investigator.

For the Screening visit only, assessments can be broken into 2 days if necessary. For all other visits, all assessments indicated must be performed on the same day.

The RC will determine eligibility of all subjects prior to enrollment. Only those subjects who fulfill all eligibility criteria will be entered into the trial.

The following assessments will be performed during the study.

10.2 Trial Assessments – Cohort 1

The following dosing days apply to subjects in Cohort 1.

D0	D0 = The first day of dosing at each monthly timepoint.
D2	D2 = The second day of dosing, 2 days after D0.

The following evaluations, as outlined in the Study Assessments Chart (see Section 3), will be performed on the days specified below:

Note:

- **Concomitant Medications should be assessed at every study visit.**
- **Adverse events (AEs) should be assessed starting at Day 1 after the first dose of trial drug.**

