10.2.14 Month 5 (D2 Visit)

Pre-injection

- Protocol refraction and visual acuity (4 meters) using ETDRS chart (SE)
- Tonometry and Ophthalmologic examination (SE)

Injection

- Zimura™ 2 mg/eye – **dose 1**
 - Indirect Ophthalmoscopy (SE) – 1 to 2 minutes after the injection to assure that the optic nerve is perfused.

- Ophthalmologic exam/Tonometry (SE) – After the injection, to confirm perfusion of the optic nerve and return of IOP to ≤ 21 mmHg or within 5 mmHg of pre-injection.
- Zimura™ 2 mg/eye – **dose 2**

Post 2nd Injection

- Indirect Ophthalmoscopy (SE) – 1 to 2 minutes after each injection to assure that the optic nerve is perfused.
- Ophthalmologic exam/Tonometry (SE) – At least 30 minutes after the second injection, a full ophthalmologic exam must be performed and IOP must be < 30 mmHg before the subject leaves the clinic.

3-Day Post-Injection Safety Check (± 1 day)

- Telephone call to subject to ensure there are no signs or symptoms of retinal detachment or endophthalmitis.

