10.5.13 Month 5 (D2 Visit)

Pre-injection

- Protocol refraction and visual acuity (4 meters) using ETDRS chart (SE)
- Tonometry and Ophthalmologic examination (SE)

Injection

- Lucentis® 0.5 mg/eye – administered 1st
 - Indirect Ophthalmoscopy (SE) – 1 to 2 minutes after the injection to assure that the optic nerve is perfused.
 - Ophthalmologic exam/Tonometry (SE) – After the injection, to confirm perfusion of the optic nerve and return of IOP to ≤ 21 mmHg or within 5 mmHg of pre-injection.
- Zimura™ 2 mg/eye – administered 2nd

Post 2nd Injection

- Indirect Ophthalmoscopy (SE) – 1 to 2 minutes after the injection to assure that the optic nerve is perfused.
- Ophthalmologic exam/Tonometry (SE) – At least 30 minutes after the second injection, a full ophthalmologic exam must be performed and IOP must be < 30 mmHg before the subject leaves the clinic.

3-Day Post-Injection Safety Check (± 1 day)

- Telephone call to subject to ensure there are no signs or symptoms of retinal detachment or endophthalmitis.

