10.5.14 Month 6 (± 7 days)/Early Withdrawal

- Vital signs
- Laboratory tests
- 12-Lead ECG
- Protocol refraction and visual acuity (4 meters) using ETDRS chart (OU)
- Goldmann applanation Tonometry and Ophthalmologic examination (OU)
- Color fundus photography (FP) (OU)

- Fluorescein Angiography (FA) (OU, transit SE)
- Spectral Domain optical coherence tomography (SD-OCT) (OU)

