### 7.1 EXTENT OF EXPOSURE

Exposure to each study medication will be evaluated for each cohort and overall with respect to treatment duration (= Last injection date – First injection date + 31, in days), number of subjects treated at each planned visit, total injections received, using descriptive statistics (N, mean, standard deviation, median, minimum, Q1, Q3, maximum).

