#### 7.4 ADVERSE EVENTS

Adverse events (AEs) will be recorded starting after the first dose of study drug and continuing until 30 days after the last dose or until the last follow-up visit required by the protocol, whichever comes later.

The safety analyses on AEs will be primarily based on the Treatment-Emergent Adverse Events (TEAEs), which is defined as an AE occurring after the first injection on Day 1 (day of the first dose of study drug) and up to and including 30 days after the last dose of study drug.

All AEs will be coded using MedDRA (Version 21.0) terms.

An overview of TEAEs will be provided. A second overview of TEAEs will be provided which displays the overall summary of TEAEs by the categories ‘Study Eye’, ‘Non-Study Eye’, and ‘Non-Ocular’. In addition, the number and percentage of patients with TEAEs will be tabulated for each treatment group and in total by system organ class (SOC) and preferred term (PT). The number and percentage of the subjects who experienced at least one TEAE will be included. Subjects will only be counted once for each preferred term. In case that a subject experienced the same event more than once, the worst severity will be presented.

Tabular summaries of the following AEs will be provided by SOC and PT:

- All TEAEs regardless of the relationship to study drugs
- All TEAEs (regardless of the relationship to study drugs) with PT occurring  $\geq 5\%$  frequency based on total subjects
- TEAEs related to study drugs
- TEAEs related to injection procedure
- TEAEs by the maximum severity grade
- Systemic TEAEs
- Systemic TEAEs related to study drugs
- Systemic TEAEs related to injection procedure
- TEAEs related to study drugs by the maximum severity grade
- TEAEs related to injection procedure by the maximum severity grade
- All Ocular TEAEs by study eye
- All Ocular TEAEs by fellow eye
- Study drug related Ocular TEAEs by study eye
- Study drug related Ocular TEAEs by fellow eye
- Injection procedure related Ocular TEAEs by study eye
- Injection procedure related Ocular TEAEs by fellow eye
- Ocular TEAEs (study eye) by the maximum severity grade
- Study drug related Ocular TEAEs (study eye) by the maximum severity grade
- Injection procedure related Ocular TEAEs (study eye) by the maximum severity grade
- TEAEs leading to discontinuation of study drug
- Study drug related TEAEs leading to discontinuation of study drug
- Injection procedure related TEAEs leading to discontinuation of study drug

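### Adverse events must be recorded to at least day 30 after the last dose, but no contact after Month 6 or Early Withdrawal is scheduled to elicit them

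*Protocol*

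**What the plan says.** Protocol 12.2 sets the recording period for adverse events as starting after the first dose and "continuing until 30 days after the last dose or until the last follow-up visit required by the protocol, whichever comes later". Protocol 12.4 uses the same end rule for SAEs. SAP 7.4 repeats the recording rule and defines a TEAE as an event after the first injection and "up to and including 30 days after the last dose of study drug". SAP 7.1 builds the same tail into exposure: "treatment duration (= Last injection date – First injection date + 31, in days".

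On the visit side, Protocol section 6 states "All subjects will have a final follow-up visit at Month 6". All four charts in Protocol section 3 end there, and the visit carries a window of 7 days either way in each cohort (10.2.15, 10.3.8, 10.4.11, 10.5.14; for Cohort 4 the heading reads "10.5.14 Month 6 (± 7 days)/Early Withdrawal"). Protocol 10.7 places the final evaluation of a discontinuing subject at discontinuation, with no minimum interval from the last injection.

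The last injections differ by cohort. Cohorts 2 and 3 receive theirs at the single Month 5 visit (10.3.7, 10.4.10). Cohorts 1 and 4 receive theirs at the Month 5 D2 visit (10.2.14, 10.5.13), where "D2 = The second day of dosing, 2 days after D0".

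**The concern.** The recording rule and the TEAE definition both run to day 30, but the calendar of contacts was not set to reach that day. After the final visit no one is scheduled to ask the subject anything. Safety is the trial's only objective, and SAP 7.4 bases the AE analysis primarily on TEAEs. An event that begins after the final visit but within 30 days of the last dose belongs in those tables, yet it would enter them only if it came to the site's attention some other way. Missed events can only lower the counts, and no planned output shows how many subjects were followed to day 30.

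**Working it through.** The plan states no figure for this interval, so there is none to reproduce. The check is calendar arithmetic.

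**Inputs**
- Required minimum: day 30 after the last dose (Protocol 12.2, 12.4; SAP 7.4).
- Offset d of the last dose from the Month 5 timepoint: 2 days in Cohorts 1 and 4, 0 days in Cohorts 2 and 3.
- Windows: 7 days either way at Month 5 and at Month 6.
- Month length L: not stated in the visible text. Assumed 28 to 31 days, with 30 as the central value.
- Window anchoring: not stated. The windows may be counted from Day 1 or from the previous visit.

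**Formula**

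Days from last dose to Month 6 = L − d − s, where s is the number of days by which the windows shorten the interval. Days without scheduled contact = 30 − (L − d − s), when positive.

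- s = 0: both visits on time.
- s = 7: Month 6 is 7 days early. This is also the most that windows anchored to the previous visit allow.
- s = 14: Month 5 is 7 days late and Month 6 is 7 days early. This is possible only if windows are counted from Day 1.

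**Results: days from last dose to Month 6 (days short of 30)**

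| Case | Cohorts | L = 28 | L = 30 | L = 31 |
|---|---|---|---|---|
| s = 0 | 1 and 4 | 26 (4) | 28 (2) | 29 (1) |
| s = 0 | 2 and 3 | 28 (2) | 30 (0) | 31 (0) |
| s = 7 | 1 and 4 | 19 (11) | 21 (9) | 22 (8) |
| s = 7 | 2 and 3 | 21 (9) | 23 (7) | 24 (6) |
| s = 14 | 1 and 4 | 12 (18) | 14 (16) | 15 (15) |
| s = 14 | 2 and 3 | 14 (16) | 16 (14) | 17 (13) |

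In Cohorts 1 and 4 (10 + 20 = 30 of 60 planned subjects), an on-time Month 6 visit falls before day 30 for every month length considered. In Cohorts 2 and 3 it does so only if the month is shorter than 30 days, and then by at most 2 days.

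**Early Withdrawal.** If this visit takes place k days after the last dose, 30 − k days remain. With no minimum for k, most of the 30 days can be uncovered.

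**Do other provisions cover the tail?**
- The three-day telephone check comes 2 to 4 days after injection and screens only for retinal detachment and endophthalmitis.
- Protocol 12.2 requires follow-up beyond the last visit only for events already ongoing then.
- Protocol 10.6 follows the event that led to withdrawal.
- Protocol 12.4 asks for later SAEs after the trial only where a causal link is suspected.

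None of these schedules a question about new events up to day 30.

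**The case against.** The strongest reply is that the recording rule is intact. By taking the later of two dates, 12.2 already allows for a final visit before day 30, and the investigator must still record any event that is volunteered, prompted or observed until then. Protocol 10.7 also has the investigator arrange follow-up of discontinued subjects where required. This stands: the gap is in scheduled ascertainment, and it would be wrong to say that events after the final visit fall outside the rule.

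The size is also easily overstated. The on-time shortfall is 1 to 4 days in Cohorts 1 and 4. The windows are symmetric, so a Month 6 visit 7 days late falls 33 to 36 days after the last dose in those cohorts (26 + 7 to 29 + 7). The 18-day extreme, 60% of the 30 days, needs a 28-day month, opposite window extremes at two visits, and counting from Day 1. It should not be read as typical.

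A reader might infer that the two-day offset biases late-event rates downward in Cohorts 1 and 4 relative to Cohorts 2 and 3. The documents do not support this. Scheduled observation from the first dose to Month 6 has the same nominal length and the same final window in all cohorts; the offset only moves the end of the 30-day definition. The TEAE tables count subjects over the whole period. Cohorts 1 and 4 also have 12 scheduled dosing days with AE assessment, against 6 in Cohort 2 and 9 in Cohort 3, so a net downward bias cannot be presumed.

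A reader might also infer that the tables claim a fully observed window. SAP section 7 says the opposite: safety values are not imputed, and summaries rest on observed cases.

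**Conclusion.** The mismatch holds as a modest gap in ascertainment. The AE, SAE and TEAE windows run to at least day 30, and no contact is scheduled after Month 6 or Early Withdrawal. With on-time visits the shortfall is 1 to 4 days in Cohorts 1 and 4 and at most 2 days in Cohorts 2 and 3, assuming months of 28 to 31 days. With a 30-day month, an early Month 6 visit raises it to 9 or 7 days. If windows are counted from Day 1, which is not stated, it can reach 16 or 14 days. Early Withdrawal has no lower limit on the interval and can leave the largest gap. Late events may therefore be under-counted. The documents give no basis for estimating by how many, and no between-cohort bias is shown.

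**What to change.** **Protocol.** In 12.2, the section 3 charts and sections 10.2.15, 10.3.8, 10.4.11 and 10.5.14, add one telephone contact on or after day 30 from the last injection for subjects whose Month 6 or Early Withdrawal visit falls earlier and who still agree to contact. The call must ask about all AEs and SAEs, so the script of the three-day check is not sufficient. State in 10.6 that the call also applies to withdrawn subjects, because that section ends protocol evaluation for those who start another NVAMD treatment before completing study dosing.

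**SAP.** In 7.4, report by cohort the number of subjects observed for the full 30 days after the last dose.

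**Cost.** A small amendment, one short call for some subjects, and a slightly later last contact. With a 30-day month the call would fall 2 days after an on-time Month 6 visit in Cohorts 1 and 4. No new visit, procedure or staff is needed.

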4.5.3 Study OPH2002

The objectives of this study were to evaluate the safety and tolerability of Zimura™ intravitreal injection in combination with VEGF therapy in subjects with idiopathic polypoidal choroidal vasculopathy (IPCV). Subjects included in the study were treatment experienced (prior treatment with anti-VEGF monotherapy of ≥ 8 injections in the previous 12 months) of either gender aged 50 years or above with diagnosis of IPCV. Subjects received 3 monthly intravitreal injections of Zimura™ (1 mg/eye) in combination with intravitreal injection of anti-VEGF agent (Avastin® 1.25 mg/eye or Lucentis® 0.5 mg/eye or Eylea® 2 mg/eye).

Safety endpoints included VA loss (proportion of subjects with > 15 letter loss at Month 30, ophthalmic adverse events (AEs), systemic adverse events (AEs), change in total retinal thickness (SD-OCT) at Month 3, regression and/or elimination of polyps at Month 3 compared to Screening as measured by indocyanine green angiography (ICGA) and laboratory values.

A total of 4 subjects were enrolled in this clinical trial and all the subjects completed the study. None of the subjects had a VA loss of more than 15 ETDRS letters at Month 3. There were no deaths during the study. There was one SAE of endophthalmitis reported in 1 subject. The SAE resolved and was assessed to be related to the injection procedure. None of the ocular AEs were assessed to be related to Zimura™ or anti-VEGF treatment.

The intravitreal administration of Zimura™ in combination with an anti-VEGF agent (Avastin®, Eylea®, or Lucentis®) in patients with IPCV was generally well tolerated. The data supports further investigation of the drug in larger clinical trials.

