5 TRIAL OBJECTIVES

5.1 Objectives

To assess the safety of intravitreal Zimura™ administered in combination with Lucentis® in treatment naïve subjects with NVAMD.

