- Ocular TEAEs (study eye) leading to discontinuation of study drug
- TEAEs leading to death
- Study drug related TEAEs leading to death
- Injection procedure related TEAEs leading to death

Ocular TEAEs has been defined as TEAEs linked to the “Eye Disorders” system organ class and the ‘Intraocular pressure increased’ preferred term.

All AEs, including non-TEAEs, will be included in individual subject listings.

The listings will include the subject identifier, age, sex, verbatim term, preferred term, eye (N/A/OD/OS/OU), serious (yes/no), date of onset, relative study day of onset, duration of the event (or continuing), severity (mild/moderate/severe), causality (relationship to study drug/injection procedure), action taken (study drug permanently discontinued: yes/no), treatment (yes/no), and outcome (resolved /unresolved / fatal).

The same listings will be provided separately for severe AEs, AEs leading to permanent discontinuation of the study drug, and for AEs leading to death.

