## 7.5 SERIOUS ADVERSE EVENTS AND DEATHS

Treatment-Emergent Serious adverse events (SAEs) will be summarized by system organ class and preferred term. The number and percentage of the subjects who experienced at least one SAE will be included.

Tabular summaries of the following SAEs will be provided:

- All SAEs regardless of the relationship to study drug
- SAEs related to study drug
- SAEs related to injection procedure
- Ocular SAEs (study eye) regardless of the relationship to study drug
- Ocular SAEs (study eye) related to study drug
- Ocular SAEs (study eye) related to injection procedure

In addition, separate listings will be created for deaths and all SAEs. List for SAEs will include the subject identifier, age, sex, verbatim term, preferred term, eye (N/A/OD/OS/OU), serious (yes/no), date of onset, relative study day of onset, duration of the event (or continuing), severity (mild/moderate/severe), causality (relationship to study drug/injection procedure), action taken (study drug permanently discontinued: yes/no), treatment (yes/no), and outcome (resolved/unresolved/fatal).

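### Causality is defined against one pooled study drug, so no planned table or listing shows the events investigators attribute to Zimura

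*Protocol*

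**What the plan says.** Protocol 12.2 gives two causality targets. An event may be related to the injection procedure "or to study drug (Zimura™ or Lucentis® 0.5 mg". The definition of a related event then treats the drug side as a single entity: "There is a reasonable possibility that the adverse event is related to the injection procedure or to the study drug".

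The SAP follows this. The tables in 7.4 are headed in the form "TEAEs related to study drugs", and those in 7.5 in the form "SAEs related to study drug". The AE listing in 7.4 carries "causality (relationship to study drug/injection procedure", and the SAE listing in 7.5 has the same item. Lucentis counts as study drug for timing too, because a treatment-emergent event is "an AE occurring after the first injection on Day 1 (day of the first dose of study drug".

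The objective in Protocol 5.1 begins: "To assess the safety of intravitreal Zimura™ administered in combination with Lucentis". The regimens in Protocol 6, 9.2.2 and 11.1 and in SAP 2.2 give both products in all four cohorts. SAP 7.1, by contrast, summarises exposure for each medication separately, so only causality is pooled.

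**The concern.** Zimura is the investigational product and Lucentis is the approved one. With no Lucentis-only arm, a count of drug-related events may reflect either product or both, and nothing in the planned output tells the reader which.

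Protocol 11.4.1 says the trial is meant to inform the safety and design of later controlled trials. For that purpose, the investigator's view on whether an event came from Zimura is cheap information, best captured when the event is reported. If it is not asked then, it cannot be reliably recovered later.

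**Working it through.** The plan states no figure on this point, so the check is a count of planned tables and planned injections.

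**Tables.** SAP 7.4 itemises 26 TEAE tables. Eight are by drug causality:
- all related events;
- related systemic events;
- related events by severity;
- related ocular events, study eye;
- related ocular events, fellow eye;
- related study-eye ocular events by severity;
- related events leading to discontinuation;
- related events leading to death.

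SAP 7.5 itemises 6 SAE tables, of which two are by drug causality (all SAEs and study-eye ocular SAEs). In total 8 + 2 = 10 of 26 + 6 = 32. All 10 are pooled and none is specific to Zimura.

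**An event before any Zimura.** In Cohort 1 the first injection is Lucentis on D0, and Zimura first follows on D2. Under the SAP 7.4 definition an event between the two is treatment-emergent, and if judged drug-related it enters the pooled tables although no Zimura has been given.

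**Planned injections per subject (regimen text).** Lucentis is 6 in every cohort. Zimura is 6×2 = 12 in Cohort 1, 6 in Cohort 2, 3×2 + 3 = 9 in Cohort 3 and 3×2 + 3×2 = 12 in Cohort 4. Total injections are therefore 18, 12, 15 and 18, so the total rises one for one with Zimura.

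**How far timing separates the drugs.** Subjects multiplied by injection days per subject:

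| Cohort | Subjects | Days per subject | Injection days | One drug only | Of these, D14 |
|---|---|---|---|---|---|
| 1 | 10 | 12 | 120 | 120 | 0 |
| 2 | 10 | 6 | 60 | 0 | 0 |
| 3 | 20 | 9 | 180 | 60 | 60 |
| 4 | 20 | 12 | 240 | 120 | 60 |
| All | 60 | | 600 | 300 | 120 |

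Of the 300 one-drug days, 60 are Lucentis only (Cohort 1 D0) and 240 are Zimura only. The one-drug days lying two days from the other drug number 300 − 120 = 180: all 120 in Cohort 1 and the 60 maintenance D0 days in Cohort 4. Adding the 300 days on which both drugs are given, 480 of 600 (80%) fall on the same day as, or two days from, the other drug. Only the 120 D14 days (20%) are further apart.

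**A dependency.** These counts use the regimen text and the protocol schedule. The SAP 3.1 schedule for Cohort 3 also marks Lucentis at the D14 visits, which contradicts SAP 2.2 and Protocol 3; the passages must be reconciled. Read literally, the SAP schedule would cut the separated days to 120 − 60 = 60 of 600 and raise Lucentis in Cohort 3 to 6 + 3 = 9.

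**The case against.** The objective concerns the combination, and relatedness to the combination is a legitimate safety summary. That stands, and it is why the pooled tables should remain. It does not make a Zimura-specific view redundant, since Zimura is the product whose safety the objective names.

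Attribution in an open-label trial is opinion, and the drugs are given close together. This also stands. A reader might take the 300 of 600 one-drug days to mean that half the events could be separated. The schedule does not support that: 180 of those days lie two days from the other drug, and even at D14 Lucentis was given only 14 days before, inside the 30 days the SAP allows for emergent events after the last dose.

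A reader might also infer that investigator attribution is the only information in the trial pointing to Zimura. It is not. All tables are by cohort, and Zimura varies from 6 to 12 injections at a fixed 6 of Lucentis. The AE listings also carry onset dates, so events could be placed against the last injection. But cohorts have 10 or 20 subjects, Cohort 1 is not randomised, and the contrast is confounded with the number of injections. It does not replace a per-event judgement.

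Finally, the sponsor's previous studies might be read as a precedent for separate reporting. They do not establish one. For OPH2000, the closest comparison, Protocol 4.5.1 describes a cataract as related to study drug. OPH2001 (4.5.2) as described gave Zimura without an anti-VEGF agent. The OPH2002 summary says "None of the ocular AEs were assessed to be related to Zimura™ or anti-VEGF treatment", which may be a joint negative statement and does not show that separate fields were collected.

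**Conclusion.** The gap is real but limited. Relatedness is defined against one pooled drug category, all 10 drug-causality tables inherit it, none of about 60 planned subjects receives Lucentis alone, and no planned AE or SAE table or listing isolates Zimura.

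A reader might go further and say that the data are recorded only in pooled form, so that no table could ever show Zimura-related events. The documents do not establish this. The AE form is not among them, Protocol 12.2 says only that relationship to trial treatment is recorded, and the form may hold a field for each drug. If it does, the general rule in SAP 3.3.1 would bring those fields into a listing, and the gap would lie in the tables and in the listing contents set out in 7.4 and 7.5.

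This is a worthwhile, low-cost improvement in reporting. It does not invalidate the planned summaries, and it would not substitute for a comparator arm.

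**What to change.** In Protocol 12.2, and on the AE form if it does not already do so, replace the single drug judgement with two yes/no items: related to Zimura, and related to Lucentis. Tick both when they cannot be separated. Keep the injection-procedure item as it is.

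In SAP 7.4 add *TEAEs related to Zimura* and *Ocular TEAEs (study eye) related to Zimura*; in SAP 7.5 add *SAEs related to Zimura*. Show both drug items in the AE and SAE listings. Keep every pooled table, defining related to study drug as either item ticked.

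The cost is one extra form field, three tables and an extra listing column. The downside is that many events will be ticked for both drugs, given the 480 of 600 injection days shown above; for those events the new tables add nothing to the pooled ones. The result remains open-label investigator opinion and should be described as such.
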